The discrepancies of the different BDNF levels might be explained by the difference of assays used. BDNF assays are now commercially available (RayBiotech, Norcross GA, USA). With this assay the minimum detectable dose of BDNF is typically less than 0.3 ng/ml without cross reactivity to other cytokines (Reproducibility - Intra-Assay: CV<10%, Inter-Assay: CV<12%).

4. Study Procedures

Study Design:

Phase 2 trial.

This selection study will be performed as a randomized, parallel Group Trial to determine the amount of FES ergometry required to achieve maximal CSF BDNF levels in individuals with inflammatory myelopathy.

Subjects will be randomized into 4 groups (FES1: 1 session of FES ergometry per week, FES3:3 sessions of FES ergometry per week, FES5: 5 sessions of FES ergometry per week, and Passive: 3 sessions of passive cycling per week). Session duration is 60 minutes. After obtaining a detailed physical and spasticity testing, baseline serum and CSF BDNF levels will be measured. The subjects will then receive

FES ergometry or passive cycling according to their group assignment for 3 weeks. At that time the subjects will return for a physical exam, spasticity testing, and repeat serum and CSF BDNF level testing. The primary investigator will be blinded to the results. The Study Time Line is found in Figure 1.

[figure not shown]

Figure 1: Study Time Line

Study Treatments

All activities will be conducted at INI and are supervised by a licensed physical therapist. This includes all cycling activities; all study procedures, the screening and final visits. Urine (for rapid urine pregnancy testing) will be sent to the Johns Hopkins Medicine (JHM) Pathology lab.

Functional Electrical Stimulation Ergometry

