After enrolling 48 subjects (12 per group) we will estimate 2 quantities: the mean BDNF CSF level per group and the within group standard deviation of BDNF levels (averaged across the 4 groups). The sample size may then be adjusted based on the estimated effect size (estimated mean per treatment group - 80% of that estimated mean) and the estimated standard deviation. If the recalculated total sample size is equal or less than 100 then the study will proceed. Otherwise the study will be terminated at that point.

The required sample size will be computed such that it provides 80% probability of correctly selecting the amount of FES that yields the highest mean BDNF given a true 20% mean difference between the highest mean and the next highest mean.

Analysis plan:

Dependent Variables: CSF BDNF concentration, Serum BDNF concentration, CSF GDNF concentration, CSF NT-3 concentration, CSF NT-4 concentration, CSF CNTF concentration, CSF NGF concentration, CSF IL-6 concentration, CSF IL17 concentration, CSF TNF α concentration, CSF IL-1 β concentration, CSF IL-23 concentration, CSF IL-12 concentration, modified Ashworth score, mood.

Independent Variables: Intervention (FES ergometry); Timing

Approach: The distributions of all outcome variables (CSF BDNF concentration, Serum BDNF concentration, CSF GDNF concentration, CSF NT-3 concentration, CSF NT-4 concentration, CSF CNTF concentration, CSF NGF concentration, CSF IL-6 concentration, CSF IL17 concentration, CSF TNF α concentration, CSF IL-1 β concentration, CSF IL-23 concentration, CSF IL-12 concentration, modified Ashworth score, mood) will be described by treatment group (mean, median, standard deviation). The group that has the highest mean change in BDNF concentration will be used for further studies (future Phase 3 clinical trial).

Exploratory analysis will be performed to compare mean values of GDNF, NT-3, NT-4, CNTF, NGF, IL-6, IL17, TNF α , IL-1 β , IL-23, IL-12 concentration among the 4 groups using analysis of variance or suitable non-parametric methods (Kruskal-Wallis Test) if the outcome appears to be non-normally distributed.

- d. Early stopping rules.

The principal investigator may discontinue the study if the interim statistical analysis as described above indicates that the number of subjects required for this trial exceeds #80.

Patients may withdraw from the study at any time for any reason. Any investigator may discontinue a patient for any of the following reasons:

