- a) The subject experiences a medical emergency that necessitates discontinuation of therapy
- b) The subject experiences a serious adverse event (WHO Grade IV-V adverse events) that is judged to be likely related to the assigned treatment group or is of severity that warrants discontinuation of assigned treatment.

Date: May 10, 2016
Principal Investigator: [name].
Application Number: NA_00041441

c) For any medical reason at the discretion of the investigator.

Individual participants will be removed from the study if they experience toxicity or complications as described above.

* Subject not compliant:

- Fails to follow directions.
- Are not compliant: participants who miss more than 3 sessions of cycling for the duration of the study.
- Unwilling to perform the second lumbar puncture prior at the end of the study.
- Become pregnant.

8. Risks

a. Medical risks, listing all procedures, their major and minor risks and expected frequency.

The medical risks are defined in the section below. This allows combining the risk and risk management in the same section for each risk.

b. Steps taken to minimize the risks.

All assessments and intervention sessions will be supervised by the Principal Investigator and/or a licensed research Physical Therapist trained in the use of FES.

For all the study procedures, the risks and risk management are defined in the sections below.

Intervention Risks:

FES

The risk associated with FES is pain at the stimulation site. **To minimize the risk**, stimulation will only be done to the participant's tolerance level. There is a minimal risk of skin burn. To further minimize the risk of skin burn, only appropriate size electrodes will be used and they will be replaced as per the manufacturer's recommendations.

The safety of FES for use during pregnancy has not been established. Therefore pregnant women will not be enrolled in the study. **To minimize the risk**, any females who are of child bearing age will be asked to undergo pregnancy testing prior to the start of the study.

Assessment Risks:

Medical History

Aside from the risk associated with disclosing personnel or protected health information outside the research study and possible discomfort with being asked personal questions, there are no known risks associated with this measurement.

Physical Exam

Date: May 10, 2016
Principal Investigator: [name].
Application Number: NA_00041441

There are no known risks associated with this assessment.

Vital Signs

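### The 80% probability of correct selection is a target that the rule as written does not assure: N counts enrolled subjects with no loss allowance, and the 100-subject limit favours optimistic interim estimates

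*Combined protocol and SAP*

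**What the plan says.** Section 4 (Study Design) describes a four-arm selection study: "This selection study will be performed as a randomized, parallel Group Trial", and "Subjects will be randomized into 4 groups".

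Section 7.c gives no SD and no N. It sets the target as follows: "The required sample size will be computed such that it provides 80% probability of correctly selecting the amount of FES". The best arm is the one with the greatest average BDNF, and its true lead over the runner-up is taken as 20%. The interim step is "After enrolling 48 subjects (12 per group) we will estimate 2 quantities", namely the group means and an averaged within-group SD. The effect is taken as 20% of an estimated mean. The study goes on if the recalculated total is at most 100. If not: "Otherwise the study will be terminated at that point".

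The Analysis plan then carries forward the arm with the largest mean change in BDNF, which can be computed only for subjects with both a baseline and a final CSF sample.

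Section 4 (removal criteria) and Section 7.d allow withdrawal for any reason. They list removals for adverse events, pregnancy and more than three missed sessions. Section 7.d adds: "Unwilling to perform the second lumbar puncture prior at the end of the study". The document gives no loss rate, inflation of N, replacement rule or analysis set. Section 7.d also gives a different threshold, 80, at which stopping is discretionary.

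**The concern.** The 80% is the only operating characteristic stated for the primary decision, and that decision picks the regimen for a Phase 3 trial. Two features of the rule push the achieved probability below it.

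- **Unit of counting.** If N enrolled subjects are needed for 80% and fewer supply a pair of CSF samples, the comparison has less information than planned. The plan itself foresees such losses. Read literally, a trigger at enrolment of the 48th subject also comes before the latest entrants have completed three weeks and given a second sample.
- **Limit of 100.** Near the limit, whether the study proceeds depends on estimates from 12 subjects per group. The trials that proceed are disproportionately those with an SD estimate that fell low or a mean estimate that fell high. Their recalculated N is then too small.

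**Working it through.** **Inputs from the protocol:** k = 4 groups; target 80%; gap δ = 20% of the highest mean; 12 per group at the interim; proceed if total N is 100 or less. **Assumed, because the protocol gives no figure:** SD/mean (CV) and loss rate. **Model:** normal data, equal SDs, random loss, the other three means tied 20% below the best (the usual design case), and level and change treated as the same variable.

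**Step 1. Reproduce the target.** With d = δ√n/SD, the probability of correct selection is ∫Φ(x+d)³φ(x)dx. Setting it to 80% gives d = 1.893, so n per group = (1.893 × SD/δ)². With a known SD and no loss, this returns 80% by construction. No N can be reproduced, since no SD is stated. At the limit, n = 100/4 = 25, so CV = 0.20 × √25/1.893 = 0.528.

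**Step 2. Loss at fixed N.** A loss ℓ multiplies d by √(1−ℓ).

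| Assumed loss | d | P(correct) |
|---|---|---|
| 0% | 1.893 | 80.0% |
| 5% | 1.845 | 78.9% |
| 10% | 1.796 | 77.8% |
| 20% | 1.693 | 75.3% |

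**Step 3. The limit, no loss.** This is a two-stage simulation with 200,000 runs per scenario and a final n never below 12 per group. The text does not say which interim mean sets the effect. The first two result columns take the highest interim mean, and the last treats the effect as known.

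| True CV | P(proceed), highest mean | P(correct given proceed), highest mean | P(correct given proceed), effect known |
|---|---|---|---|
| 0.40 | 0.99 | 82.2% | 80.6% |
| 0.45 | 0.91 | 80.8% | – |
| 0.50 | 0.74 | 79.4% | 77.9% |
| 0.528 | 0.62 | 78.9% | 76.7% |
| 0.60 | 0.35 | 77.0% | 72.1% |

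At CV 0.528, the SD estimate among trials that proceed averages 0.91-0.95 of the truth across the two versions. In the highest-mean version, the interim mean is also 8-17% too high at CV 0.50-0.60. Both errors shrink N.

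**Step 4. Limit and loss together, true required N = 100 (CV 0.528), given proceed.**

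| Assumed loss | Effect known | Effect from highest interim mean |
|---|---|---|
| 0% | 76.7% | 78.9% |
| 10% | 74.2% | 76.0% |
| 20% | 71.2% | 72.8% |

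**Step 5. Cost of counting pairs.** A first stage of 48 pairs needs 48/0.9 = 53.3, so 54 enrolled at 10% loss, and 48/0.8 = 60 at 20%. If 100 stays the limit on enrolment, 90 or 80 pairs are available. The largest CV compatible with 80% falls from 0.528 to 0.20 × √22.5/1.893 = 0.50, or 0.20 × √20/1.893 = 0.47.

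**The case against.** The strongest reply is that the 80% is written as a target for N, not as a property of the whole two-stage rule, and that no arithmetic in the plan is wrong. That is correct. A reader might infer that the rule never delivers 80%. The documents do not support this: with no loss and a CV up to about 0.42-0.47 it gives about 80% or more. But Section 7.c says there is too little information on CSF BDNF to compute a sample size, so the sponsor cannot claim to be in that region.

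Second, the result depends on which interim mean sets the effect. If it is the average of the four, then in the tied case that average is (1 + 3 × 0.8)/4 = 0.85 of the best, and n rises by 1/0.85² = 1.38. Away from the limit this would absorb a 20% loss (1.38 × 0.8 = 1.10), at the price of stopping more often. The plan does not choose this reading.

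Third, the tied configuration is unfavourable. If the four means were equally spaced 20% apart, the same n would give 90.8% with no loss and 88.1% with 20%. The hypothesis in Section 2 favours five sessions, but the stated condition fixes only the gap between the best and the next best.

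Fourth, loss may be small. Exclusion 5 screens out subjects unwilling to have two punctures, an FES trial comes before baseline, and treatment lasts three weeks. So loss is not certain, and 5% costs only about one point. Section 7.d nevertheless provides for later refusal. Losses may also differ by arm: FES1 has three sessions in total, so the missed-session rule cannot remove anyone there, whereas FES5 has fifteen.

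**Conclusion.** The point holds as a lack of assurance, not as an error of calculation. Loss alone lowers the 80% to about 78.9, 77.8 or 75.3% at an assumed 5, 10 or 20%. The limit alone costs about 1-3 points near a true required N of 100. Together they give about 74-76% at 10% loss and 71-73% at 20%. These figures rest on the assumed CV and loss rates and on the model in the working. The size is modest and uncertain; the direction near the limit is not.

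A reader might also infer that a regimen will be chosen from a study stopped at 48, because the selection sentence carries no condition. The documents do not say so, and termination can fairly be read as no selection. This is an ambiguity to close. It is worth closing because, at a true required N of 100, such a pick would be right only about 55-65% of the time, depending on how the effect is set.

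**What to change.** (a) In Section 7.c, trigger the re-estimation when 12 subjects per group have paired CSF samples. Express the recalculated N in paired-CSF subjects, and compare N/(1 − observed loss) with the existing upper limit. The cost is a few more first-stage enrolments (about 54 at 10% loss, 60 at 20%), each facing two lumbar punctures, and a somewhat greater chance of stopping. The upper limit on enrolment does not rise.

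(b) Describe the 80% as nominal. Report the simulated probability of correct selection over a grid of CV and loss rather than as one range. Simulate the plan's own rule, with the effect estimated from the interim mean, and name which mean is used. The text sizes on BDNF level but selects on change, so state which variable's SD enters.

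(c) As a clarification only, add that if the study is terminated at the re-estimation no regimen is selected, and arm estimates with 95% intervals are reported.

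The thresholds of 100 in Section 7.c and 80 in Section 7.d must be reconciled before the simulation is run. Otherwise the work is plan wording and one simulation, and a stated figure may become slightly less favourable.

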This is a routine exam performed for people with spinal cord injury. Muscle tone will be assessed using the Modified Ashworth Scale (MAS). The MAS is a widely used neurological rating scale, ranging from 0 (normal) to 5 (rigidity). It measures neurological impairment and disability based on the ratings of an observer or neurologist through structured definitions. The MAS will be conducted by the study neurologist at baseline and at the final study visit.

e) Fast Urine Pregnancy Test:

This is a routine exam performed for women of child bearing age who do not take any birth control prophylaxis. Urine samples will be obtained at KKI. The urine (for rapid urine pregnancy testing) will be sent to the Johns Hopkins Medicine (JHM) Pathology lab.

f) Concomitant Medications

This is a routine exam performed for people with spinal cord injury. Concomitant medications will be recorded.

g) FES Trial

This is a routine exam performed for people with spinal cord injury at the ICSCI. Once medically screened to continue participation in the study, subject will undergo a trial use of the FES cycle. This trial of FES will be overseen by a trained physical therapist experienced at setting up the FES cycle. The goal of this will be to ensure that the patient is willing and able to use the cycle.

h) CSF Analyses via Lumbar Puncture

This is a routine procedure with an experimental analysis. Cerebrospinal fluid (CSF) will be collected by one of the study investigators at KKI. Approximately 12-15ml of CSF will be collected during each procedure.

Neural activity triggered by FES may induce an increase in nerve growth factors, or neurotrophins as described in the background section of this document. Such factors, including brain derived neurotrophic

Date: May 10, 2016

Principal Investigator: [name].

Application Number: NA_00041441

factor (BDNF), nerve growth factor (NGF), ciliary neurotrophic factor (CNTF), glial cell line-derived neurotrophic factor (GDNF), neurotrophin-4 (NT4), and neurotrophin-3 (NT3) have been shown to decrease after cessation of neural activity. BDNF has been linked to improved functional outcomes following CNS injury. We therefore chose BDNF as a surrogate marker to determine FES efficacy. In addition to BDNF we will also look at several other neurotrophins and inflammatory markers as noted above.

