Most individuals with inflammatory myelopathy have lost normal voluntary control of lower extremity function. Functional Electrical Stimulation cycling with the RT-300 allows the equivalent of 6000 step cycles in one hour (when cycling at 50 rpm), a little over half the normal number of steps a healthy adult takes on average per day. Six lower extremity muscle groups are simultaneously stimulated with this device. It is therefore the most efficient device in delivering electrical stimulation to subjects with complete spinal cord injury and was therefore chosen for this study.

The RT-300 FES bike has been FDA-cleared for use in general rehabilitation (the device clearance number is K072398). It has been a standard rehabilitation treatment modality at our center for several years.

7. Study Statistics

- a. Primary outcome variable.

BDNF CSF level testing

BDNF levels in the CSF of the study subjects will be measured in response to FES ergometry. BDNF has been linked to improved functional outcomes following CNS injury. We therefore chose BDNF as a surrogate marker to determine FES efficacy.

- b. Secondary outcome variables.

CSF analysis

Exploratory analysis to further understand the CSF response to FES cycle ergometry. It will be aimed at examining neurotrophins and define the molecular signature of repair in the CSF of patients with spinal cord injury.

Spasticity level:

Date: May 10, 2016
Principal Investigator: [name].
Application Number: NA_00041441

FES cycle ergometer therapy is expected to improve spasticity. This will be assessed by Modified Ashworth testing.

- c. Statistical plan including sample size justification and interim data analysis.

Sample size and power:

This is a dose finding clinical trial. Because there is limited data on BDNF CSF levels, the sample size cannot be computed at this time (power analysis cannot be performed). Instead we will use an adaptive sample size re-estimation strategy. Based on *in vivo* BDNF animal data we decided an effect size of 20% to be significant⁸⁰.

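### Spasticity is a secondary outcome that FES is expected to improve, but no prespecified analysis of the Modified Ashworth score evaluates that expectation

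*Combined protocol and SAP*

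**What the plan says.** Section 7.b lists two secondary outcomes, CSF analysis and spasticity level. For the second it says: "FES cycle ergometer therapy is expected to improve spasticity. This will be assessed by Modified Ashworth testing".

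Section 4, Study Assessments, item d describes the scale as an observer rating from 0 to 5 and fixes its timing: "The MAS will be conducted by the study neurologist at baseline and at the final study visit". The visit lists and Table 1 agree. No muscles, sides or summary score are named.

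Section 7.c lists the Modified Ashworth score as a dependent variable, and the intervention and timing as independent variables. The Approach paragraph then gives two kinds of analysis:

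- Description of all outcomes, the Modified Ashworth score among them, which "will be described by treatment group (mean, median, standard deviation").
- A between-group comparison that begins "Exploratory analysis will be performed to compare mean values of GDNF, NT-3, NT-4, CNTF, NGF, IL-6, IL17" and continues through the remaining cytokines. Its method is stated for "concentration among the 4 groups using analysis of variance or suitable non-parametric methods (Kruskal-Wallis Test"). The Modified Ashworth score is not in this list.

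Change from baseline appears once in the Approach paragraph, for BDNF only: "The group that has the highest mean change in BDNF concentration will be used for further studies".

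**The concern.** One of the two secondary outcomes gets a between-group comparison. The other, which carries a directional expectation, gets a mean, median and SD per arm. A fall in the score within an FES arm could come from stimulation, from cycling movement alone, from regression to the mean or from drift in rating. Separating these needs a contrast between randomised arms with a measure of uncertainty, and none is planned.

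Two omissions add to this. The baseline rating is collected but enters no stated model, since timing is listed as a factor without being tied to any analysis. The score is also treated as one variable although the scale can be applied to several muscle groups on two sides. The way ratings are combined could therefore be settled after the data are seen.

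At stake is whether the trial's statement about spasticity at Week 3 rests on a planned estimate or on reading four columns of summaries. The dose selection is not affected, because it depends on BDNF.

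**Working it through.** **Text check.** The places that bear on this outcome, side by side:

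| Place | Content on spasticity or the Modified Ashworth score |
|---|---|
| Section 2, Objectives | Not mentioned |
| Section 4, item d, visit lists and Table 1 | Measured at baseline and Week 3 |
| Section 4, justification for the control group | Passive arm justified by CSF neurotrophin levels; no functional difference expected between active and passive groups in a 3-week study |
| Section 7.b | Secondary outcome, improvement expected, no comparator named |
| Section 7.c, description | Mean, median and SD by treatment group |
| Section 7.c, comparison | Not among the 11 markers (GDNF, NT-3, NT-4, CNTF, NGF, IL-6, IL-17, TNF-α, IL-1β, IL-23, IL-12) |

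The documents give no SD, effect size, power or sample size for this score, so there is no stated figure to reproduce. Section 7.c says that no power analysis can be done at the outset.

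**Illustrative precision.** Inputs:

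- n = 12 per arm (48 in four groups, section 7.c).
- n = 25 per arm, from the ceiling of 100 in section 7.c (100/4).
- n = 20 per arm, from the figure of 80 in section 7.d (80/4). It is included because the two sections give different ceilings.
- r, the correlation between baseline and Week 3 scores: assumed 0.5 or 0.7, because the documents give none.

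For a pairwise contrast from a four-arm linear model, in units of the within-arm SD:

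half-width = t(0.975, df) × √(2/n) × √(1 − r²)

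Here df = 4n − 4 without baseline and 4n − 5 with it. For r = 0.5 the last factor is √0.75 = 0.866, and for r = 0.7 it is √0.51 = 0.714.

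- n = 12, Week 3 only: 2.015 × 0.408 = 0.82
- n = 12, r = 0.5: 2.017 × 0.408 × 0.866 = 0.71
- n = 12, r = 0.7: 2.017 × 0.408 × 0.714 = 0.59

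| n per arm | Week 3 only | r = 0.5 | r = 0.7 |
|---|---|---|---|
| 12 | 0.82 | 0.71 | 0.59 |
| 20 | 0.63 | 0.55 | 0.45 |
| 25 | 0.56 | 0.49 | 0.40 |

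With two-sided alpha 0.05 and 80% power (both assumed) and a normal approximation, the detectable pairwise difference at 12 per arm is (1.96 + 0.84) × 0.408 = 1.14 SD on Week 3 scores alone. Multiplying by 0.866 or 0.714 gives 0.99 or 0.82 SD with baseline adjustment.

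The comparison would therefore be imprecise. That favours an estimate with an interval over a powered test. Baseline adjustment shortens the interval by about 13% (1 − 0.866) or 29% (1 − 0.714).

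**The case against.** The strongest reply is that description is a legitimate choice here. This is a selection study whose decision rule uses CSF BDNF. Spasticity is absent from the objectives and has no formal hypothesis, and section 4 expects no functional difference between active and passive groups at 3 weeks. Even the CSF comparisons are called exploratory, and an added model at 12 per arm would seldom settle the matter. All of this stands. It limits the weight of the point and means that any added analysis should be labelled exploratory. It does not explain why section 7.b states an expected improvement and section 7.c plans nothing that addresses it.

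A reader might infer three stronger things that the documents do not support:

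- *That the expectation cannot be evaluated at all.* The four arms are summarised side by side. With the group sizes, the means and SDs are enough for an informal unadjusted contrast. What is missing is a prespecified one.
- *That the Passive arm was included to isolate an FES effect on spasticity and is then ignored.* Section 4 justifies it by neurotrophin levels, and it is one of the four groups described. It is available for this comparison but was not designed for it.
- *That the plan disregards the baseline.* Listing timing as an independent variable suggests that a before/after view was intended. It was not specified.

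It is also fair to say that section 7.b names no comparator, so reading the expectation as FES versus Passive is only one interpretation. The plan needs to say which it means.

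**Conclusion.** The point holds in a limited form. A named secondary outcome with a stated direction, measured at both visits by raters whom section 4 describes as blinded, has no prespecified comparison, interval or baseline adjustment. Its summary score is undefined. This should be corrected, but it does not threaten the primary selection.

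The textual finding needs no assumption. The sizes do: the half-widths of 0.59 to 0.82 SD at 12 per arm, and 0.40 to 0.56 SD at 25, assume a linear model with equal variances, all randomised participants contributing, and correlations of 0, 0.5 and 0.7 that the documents do not give. They apply to a linear ANCOVA and do not carry over to a rank or odds scale.

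Sections 4 and 7.b also need to be reconciled. If spasticity counts as function, the expected improvement, read as FES versus Passive, conflicts with the statement that no functional difference is expected. If the expectation is within group, there is no conflict, but the text should say so.

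**What to change.** In section 7.c:

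1. Define the Modified Ashworth summary as the mean rating over a set of leg muscle groups named in advance, both sides.
2. Compare Week 3 scores among the four arms with one prespecified model, an ANCOVA adjusted for the baseline score. Because the rating is ordinal, add a rank-based version as a sensitivity analysis.
3. Report each FES arm versus Passive with an estimate and 95% confidence interval. Note that FES3 versus Passive matches the number of sessions (9 each over 3 weeks).
4. Label the analysis exploratory and unpowered.

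In section 7.b, state whether the expected improvement is within group or relative to Passive, and reconcile it with the statement on functional differences in section 4.

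The cost is some wording and one extra exploratory model on data already scheduled at both visits. The downside is limited precision, so a wide interval that includes no difference should not be read as evidence of no effect.

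### Selecting on raw mean change uses the baseline CSF BDNF inefficiently, and the 80% target, sized on the SD of levels, fits that rule only if the two visits correlate at 0.5

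*Combined protocol and SAP*

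**What the plan says.** - **Selection rule** (section 7.c, Analysis plan): "The group that has the highest mean change in BDNF concentration will be used for further studies". The mean is a plain group mean of change; no covariate is named.
- **Model terms** (same place): "Independent Variables: Intervention (FES ergometry); Timing". Baseline BDNF is not listed as a covariate there or elsewhere.
- **Data available** (section 4, Study Design): "baseline serum and CSF BDNF levels will be measured", and both are measured again after three weeks. Table 1 schedules a lumbar puncture at the Baseline and Final visits. Both values therefore exist for every subject who completes both punctures.
- **Target** (section 7.c, Sample size and power): the size is to be chosen so "it provides 80% probability of correctly selecting the amount of FES that yields the highest mean BDNF". The best group is assumed to exceed the runner-up by 20%.
- **Sizing input** (same place): "After enrolling 48 subjects (12 per group) we will estimate 2 quantities". These are the group mean BDNF level and "the within group standard deviation of BDNF levels (averaged across the 4 groups". Neither the SD of change nor the SD left after baseline adjustment is mentioned.
- **Cap** (same place): "If the recalculated total sample size is equal or less than 100 then the study will proceed". Section 7.d gives 80 instead of 100; those two figures need to be reconciled separately.

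**The concern.** The trial exists to rank four groups and carry one forward, so the precision of the ranking statistic is what the design buys with two lumbar punctures per subject.

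Subtracting the baseline is the right adjustment only if a one-unit higher baseline predicts a one-unit higher Week 3 value. With any weaker relationship, the change score adds baseline noise that an estimated slope would not.

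Separately, the number of subjects is derived from the spread of BDNF levels, but the decision uses the spread of BDNF changes. These spreads agree only in a special case, so the stated 80% may not describe the rule that will be applied. Because the re-estimated size also decides whether the study continues past the interim, the choice of SD affects that decision too.

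**Working it through.** **Inputs from the documents.** Four groups; 12 per group at the interim; a cap of 100 (25 per group) or 80 (20 per group); target 80% correct selection; a 20% gap between the best and next-best mean.

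**Assumptions.** The documents give no SD, no final size and no Baseline-to-Week-3 correlation rho. I assume approximately normal group means, the same SD at both visits and in all groups, and the other means tied just below the best (the least favourable case). I vary rho.

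**1. The plan's 80%.** For k groups with n each, gap d and SD s, the probability of correct selection is

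PCS(h) = ∫ Φ(x+h)^(k−1) φ(x) dx, with h = d√n/s.

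For k = 4, PCS = 80% at h = 1.893. The 80% cannot be reproduced without an SD. It can only be back-solved: with d equal to 20% of the highest mean, the largest coefficient of variation that meets the target is 0.2√n/1.893. That is 0.37 at n = 12, 0.47 at n = 20 and 0.53 at n = 25.

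**2. Variance of each statistic.** Randomisation gives the groups the same expected baseline, so d is the same for all three statistics. Per-subject variance, in units of s²:

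- Week 3 level alone: 1
- change: 2(1−rho)
- ANCOVA: 1−rho²

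The ratio of ANCOVA to change is (1−rho²)/[2(1−rho)] = (1+rho)/2. With unequal SDs s1 (Baseline) and s2 (Week 3), change exceeds ANCOVA by (s1 − rho·s2)², which is never negative, so the direction does not depend on equal SDs.

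**3. If change scores gave exactly 80%.** ANCOVA on the same subjects has h = 1.893/√[(1+rho)/2].

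| rho | ratio | h | PCS, 4 groups |
|---|---|---|---|
| 0.3 | 0.65 | 2.348 | 88.5% |
| 0.5 | 0.75 | 2.186 | 85.8% |
| 0.7 | 0.85 | 2.053 | 83.4% (83.35) |
| 0.9 | 0.95 | 1.942 | 81.1% |

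With three candidates (80% at h = 1.652), the first three rows become 87.4%, 85.0% and 82.9%.

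**4. If the trial is sized as the plan says, on the SD of levels.** Then h = 1.893 for the Week 3 level, 1.893/√[2(1−rho)] for change and 1.893/√(1−rho²) for ANCOVA.

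| rho | change | ANCOVA |
|---|---|---|
| 0 | 65.6% | 80.0% |
| 0.3 | 72.9% | 82.0% |
| 0.5 | 80.0% | 85.8% |
| 0.7 | 89.9% | 92.5% |
| 0.9 | 99.6% | 99.7% |

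Change meets 80% exactly only where 2(1−rho) = 1, that is rho = 0.5.

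**5. In subjects.** If the levels-based size is 25 per group, 80% at rho 0.3 needs 25 × 1.4 = 35 per group with change and 25 × 0.91 = 22.75, so 23, with ANCOVA. At rho 0.5 it is 25 against 25 × 0.75 = 18.75, so 19.

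**6. Cost of estimating the slope.** With 48 subjects in four groups, 44 degrees of freedom remain within groups. The expected variance inflation for a difference between groups is 1 + 1/(44−2) = 1.024. At rho 0 this lowers h to 1.893/√1.024 = 1.871, a PCS of about 79.5%. At 12 per group ANCOVA is no worse than change until (1+rho)/2 = 42/43, which is rho of about 0.95.

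**The case against.** **The rule matches the objective.** The primary objective is an increase in CSF BDNF, and mean change measures that directly. This is fair, but nothing is lost by adjusting: with a common slope, regressing Week 3 or change on group and Baseline gives identical group differences.

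**Rho may be high.** Section 3 gives assay CVs below 10% (intra) and 12% (inter), and section 4 has the samples analysed in pairs. If the between-subject CV were 50% (my assumption) and assay noise the only noise, rho would be about 1 − (0.12/0.5)² = 0.94 to 1 − (0.10/0.5)² = 0.96, and the gain about half a point. This stands as a limit on size. The larger gains need day-to-day variation or varied individual response, for which the documents give no figure. In the other direction, two adult CSF means cited in section 3 (6.16 and 242 pg/ml) lie below the assay's quoted detection limit (typically less than 0.3 ng/ml, that is 300 pg/ml). Readings near that limit would lower rho.

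**Stronger readings that do not hold.**

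- A reader might infer that the baseline is thrown away. It is not: change uses it with slope 1, and above rho 0.5 change beats the Week 3 level alone.
- A reader might infer a bias towards a group that starts low. Given a chance imbalance, change does favour that group, but under randomisation the expected difference is unbiased. The imbalance is already counted in the variance ratio, so it is not a second harm.
- A reader might infer that the trial will miss 80%. That follows only if rho is below 0.5; above it the stated rule exceeds 80%.

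**Skewed levels.** The formulas assume roughly normal means. If levels are skewed, raw-scale ANCOVA recovers less than the tables show, which is why the scale must be named.

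**Conclusion.** The point holds as a free improvement; it is not an error that invalidates the selection. The direction is secure: the baseline-adjusted mean is at least as precise as raw change, apart from a very small slope-estimation cost when rho is about 0.95 or more at 12 per group. The size is not secure, because it depends on a rho that the documents do not give. The gain is worth having at low to moderate rho and negligible near 0.9.

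The mismatch between sizing and selection can be read directly from the plan. Under the stated assumptions, the 80% does not describe the change-score rule except at rho 0.5, whereas the baseline-adjusted mean holds the target at every non-negative rho, up to the half point that slope estimation costs near rho 0.

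Whether the passive group can be the one selected is a separate question. Section 7.c speaks of the group in the selection rule but of the amount of FES in the target. Nothing here settles that, and the conclusion is the same for three or four candidates.

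**What to change.** In section 7.c, Analysis plan, replace the selection sentence with wording such as:

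> The group with the highest baseline-adjusted mean Week 3 CSF BDNF (ANCOVA of the Week 3 value on group and Baseline value, on the log scale if levels are skewed) is carried forward. Raw mean change by group is reported as supportive.

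In Sample size and power, replace the within-group SD of levels with the residual SD from that same model, so that the 80% refers to the statistic used for selection. If the log scale is used, take the SD on that scale. The plan's gap (a mean against 80% of it) becomes −ln(0.8) = 0.223.

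State in advance how the scale is chosen and how values below the detection limit are handled. Keep the word group, so that the edit does not change who can be selected.

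The cost is a few sentences in 7.c and one extra model fit at the interim. No further subjects, visits, samples or lumbar punctures are needed.
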